Statistical Analysis	
Randomization: 120 patients will be recruited into the study and randomized to either 0.50 mg/kg Relteceimod or placebo in a 1:1 ratio. Randomization will be performed within site and according to two stratification variables.
 
• Acuity of AKI: whether or not AKI is diagnosed at time of presentation of abdominal infection or surgical confirmation of NSTI; or during the 48 hours following the suspected diagnosis of abdominal infection or surgical confirmation of NSTI.• Subject Age: ≥ 18 to ≤ 75 or > 75 to ≤ 85 years old. 
Four computer generated, blocked randomization lists will be provided for each site, one for each of four strata defined on the basis of the 2 by 2 cross-tabulation of the two stratification variables. Within each block, half of the assignments will be to active drug and half to placebo, in random order. Block sizes will be varied.
 
Blinding: The study will remain blinded as to treatment allocation. The actual randomized treatment allocations will be kept by a contracted third-party responsible only for managing the randomization process. A variable indicating the blinded treatment allocations will not be part of the clinical study data to be managed by the data management clinical research organization (CRO). Therefore, only blinded study data will be available to the primary study statistician and responsible primary programming staff.
 
Analysis Sets:
 
• The intent-to-treat (ITT) analysis set will include all randomized patients.• The As-Treated (AT) analysis set will include all randomized patients who were exposed to study medication (active or placebo). The AT analysis set will be used in the primary safety analyses with patients assigned to actual treatment received.• The modified intent-to-treat (mITT) analysis will include all randomized patients who were exposed to study medication (active or placebo) and had a definitive diagnosis of abdominal sepsis or NSTI with patients assigned to their intended randomized assignment. The mITT set will be used in primary effectiveness comparisons.• Supporting effectiveness analyses may be performed using a Per Protocol (PP) analysis set. 
Primary Analysis: The primary efficacy comparison involves testing the following superiority hypotheses: H₀: $\pi_{0.50} - \pi_{\text{Placebo}} \leq 0$ vs H_a: $\pi_{0.50} - \pi_{\text{Placebo}} > 0$; where $\pi_{0.50}$ and π_{Placebo} represent the true probability of freedom from durable loss of eGFR (alive, free of dialysis, and less than a 37% loss of eGFR (measured with the MDRD formula from the patient's reference eGFR)) at Day 28. Each probability represents the proportion of subjects on each arm expected to achieve freedom from durable loss of renal function. These hypotheses will be tested using an unadjusted chi-square test at a one-sided type 1 error rate of $\alpha=0.025$. The null hypothesis will only be rejected if the proportion of responders is larger in the active drug group compared to placebo.
 
Sample Size Justification: This trial will enroll 120 subjects that will be randomized in a ratio of 1:1 to either Relteceimod 0.50 mg/kg (n=60) or placebo (n=60), each in addition to SoC. Sample size analysis was performed assuming that all patients will be evaluable for the primary endpoint using last observation carried forward (LOCF) for patients missing a serum creatinine value on Day 28.

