-----------------------------	--

	
The primary efficacy hypothesis will be tested using an unadjusted χ^2 statistic with a one-sided $\alpha=0.025$ significance level. The null hypothesis will only be rejected if the investigational drug demonstrates superiority. Statistical power was computed for a range of expected treatment group differences supported by the results of preliminary studies. Based on preliminary data, a total of 120 patients will be enrolled. This sample size results in 89% power if the true success rates are 75% and 50% for the investigational drug and placebo, respectively.
 
Sample Size Re-Estimation: A “Promising Zone” sample size re-estimation interim analysis is planned for when between 50% and 67% of the initial sample size is evaluable for the primary efficacy endpoint⁵³). The purpose of the sample size re-estimation is to maintain (conditional) power when the treatment group difference is smaller than 0.25, but still clinically meaningful.
 
A pre-specified maximum sample size expansion will be specified prior to providing unblinded results to the independent data monitoring committee (iDMC) but in no case will the sample size expansion exceed an additional 200 subjects. With this restriction, only clinically meaningful treatment effects are detectable with good statistical power at the maximum sample size. The specific rules for determining if sample size expansion is permissible and if so, by how much, will ensure control of type 1 error.
 
Specifically, the sample size will be increased up to the maximum to maintain conditional power to as close to 80% as possible, but only if conditional power at the interim analysis is above a pre-specified threshold that results in control of type 1 error to the desired nominal value. If conditional power falls within the Promising Zone, increasing the sample size up to the pre-specified maximum is at the discretion of the Sponsor.
 
Futility Analysis: In addition to sample size re-estimation, a non-binding futility analysis will be conducted at the time of the interim analysis. If conditional power is below a pre-specified futility threshold, enrollment may be immediately stopped at the discretion of the Sponsor.
 
Independent Data Monitoring Committee (iDMC): A detailed iDMC charter will be provided to clarify all relevant issues relating to the conduct of the sample size re-estimation and futility analysis, including specific details regarding the operational procedures with fire-walls to protect against potential operational biases, decision rules, composition of the iDMC members and their conflict of interest statements.
 
Adjudication Committee for Evaluation of AKI Stage and Recovery: Experts chosen for the AKI Adjudication Committee will be independent of the Sponsor and neither they nor their institutions participated in the sample collection or sample measurement studies. Each adjudicator will be provided a form for each patient containing all relevant clinical information. Adjudicators will be blinded to group assignment and clinical data will be identified only by anonymized identification number. Adjudicators will indicate their assessment of AKI staging and recovery independently without consultation with each other. The basis for the adjudication will be the KDIGO consensus criteria corresponding to Stages 1-3 (mild to severe). A two thirds majority was predefined for use as the final adjudication.
 
Secondary Endpoints: Secondary endpoints have been specified from several domains including a similar endpoint but defined at Day 14. Additional secondary endpoints include time to the primary endpoint, AKI free days, SOFA over time, and critical care and hospital stay parameters (hospital length of stay (LOS), ICU and ICU-free days, ventilator days and –free days, vasopressor days and –free

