12.5 Synopsis of Key Statistical Approaches

12.5.1 Primary Efficacy Comparison

The primary efficacy comparison involves testing the following one-sided superiority hypotheses: **H₀: $\pi_{0.50} - \pi_{\text{placebo}} \leq 0$ vs H_a: $\pi_{0.50} - \pi_{\text{placebo}} > 0$** ; where $\pi_{0.50}$ and π_{placebo} represent the true probability of freedom from durable loss of kidney function (alive, free of dialysis, and less than a 37% loss of eGFR (measured with the MDRD formula from the patient's reference eGFR)) at Day 28. Each probability represents the proportion of subjects on each arm expected to achieve freedom from durable loss of renal function. These

hypotheses will be tested using an unadjusted chi-square test at a one-sided type 1 error rate of $\alpha=0.025$. The null hypothesis will only be rejected if the proportion of responders is larger in the active drug group compared to placebo. It is a noteworthy advantage of the sample size re-estimation approach to be used (see details below) that the conventional test statistic may be used to test the primary hypothesis and there is no need to weight subjects randomized after the sample size re-estimation differently from those randomized before the sample size re-estimation.

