10	Deviations from the Original Statistical Plan.....	42
11	Appendix 1: Tables and Listing TOC.....	43
12	Appendix 2: AE Listings.....	52
13	Appendix 3: Patient Listings.....	53
14	Appendix 5: Study Visits and Procedures.....	55
15	Appendix 6: Clinical Score Calculations.....	60
15.1	AKI Staging (KDIGO Criteria).....	60
15.2	Twice the Serum Creatinine for Age, Race, and Gender.....	61
15.3	SOFA – Sequential Organ Failure Assessment Score.....	62
16	Appendix 7: Prior and Concomitant Medications.....	63
16.1	Nephrotoxic Medications.....	63
16.2	Immunosuppressant Medications.....	63
17	Appendix 8: CKD Definition and Classification.....	66
17.1	CKD Definition:.....	66
17.2	CKD Classification.....	66

1 Purpose and Scope of SAP

The purpose of this Statistical Analysis Plan (SAP) is to provide details regarding the analyses sets, endpoints, and statistical analysis methods to be used to meet the objectives of this trial. When differences exist in descriptions or explanations in the Clinical Study Protocol and this SAP, the SAP prevails. This SAP will be finalized prior to unblinding of the treatment allocation codes.

This document is designed to be a stand-alone document in terms of conveying essential statistical approaches to the analysis of the data. Additional definitions and details regarding variables collected are provided in the Clinical Study Protocol.

Statistical approaches were developed to be consistent with accepted statistical and clinical trial principles including ICH E9, Statistical Principles for Clinical Trials¹.

¹ ICH E9 Expert Working Group. Statistical Principles for Clinical Trials: ICH Harmonized Tripartite Guideline. *Statistics in Medicine* 1999; 18:1905–1942.

2 Key Elements of the Analysis Plan

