2.1 Primary Efficacy Analysis

2.1.1 Primary Superiority Hypothesis

The primary effectiveness endpoint is *freedom from durable loss of renal function at Day 28*. Success requires:

- Alive at Day 28,
- Free of dialysis at Day 28, and
- Less than a 37% loss of estimated Glomerular Filtration Rate (eGFR; measured with the Modification of Diet in Renal Disease (MDRD) formula from the patient's reference eGFR) at Day 28.

Reference creatinine values, baseline AKI stage and percentage loss of eGFR will be determined through algorithmic determination (see details below). Percentage loss of eGFR determined algorithmically will be based on a comparison of eGFR at screening compared to an algorithmically determined reference creatinine value.

The primary efficacy comparison involves testing the following one-sided superiority hypotheses: **H₀: $\pi_{0.50} - \pi_{\text{placebo}} \leq 0$ vs H_a: $\pi_{0.50} - \pi_{\text{placebo}} > 0$** ; where $\pi_{0.50}$ and π_{placebo} represent the true probability of freedom from durable loss of renal function at Day 28. Each probability represents the proportion of subjects on each arm expected to achieve complete recovery. These hypotheses will be tested using a one-sided type 1 error rate of $\alpha=0.05$. The null hypothesis will only be rejected if the investigational drug demonstrates superiority. An unadjusted chi-square test will be used to test this hypothesis.

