2.1.2 Sample Size Justification

This trial will enroll 120 subjects randomized in a 1:1 ratio to either Reltecimod 0.5 mg/kg (n=60) or placebo (n=60), both in addition to standard of care (SoC). Sample size analysis was performed assuming all patients will be evaluable for the primary endpoint due to using last observation carried forward (LOCF) for patients missing the creatinine value on Day 28. The primary efficacy hypothesis will be tested using an unadjusted χ^2 statistic with a one-sided $\alpha=0.05$ significance level. Rejection of the null hypothesis will only occur if investigational drug superiority is demonstrated. Statistical power was computed for a range of expected treatment group differences supported by the results of preliminary studies. The following table summarizes the statistical power for a total sample size of N=120 (60 per group) for various assumptions regarding the success rate in the investigational arm and assuming a success probability of 0.50 among controls. This sample size results in 89% power if the true success rates are 75% and 50% for the investigational drug and placebo, respectively, for a group difference of 25%. Power remains above 80% if the true group difference is at least 22% (Table 1).

Table 1. Computed Power			
Index	Control	AB103	Power
1	0.5	0.65	0.507
2	0.5	0.70	0.727
3	0.5	0.71	0.766
4	0.5	0.72	0.802
5	0.5	0.73	0.834
6	0.5	0.74	0.864
7	0.5	0.75	0.890

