5.2 Primary Endpoint

The primary efficacy comparison involves testing the following one-sided superiority hypotheses: **H₀**: $\pi_{0.50} - \pi_{\text{placebo}} \leq 0$ vs **H_a**: $\pi_{0.50} - \pi_{\text{placebo}} > 0$; where $\pi_{0.50}$ and π_{placebo} represent the true probability of freedom from durable loss of renal function at Day 28. Each probability represents the proportion of subjects on each arm expected to achieve complete recovery. These hypotheses will be tested using a one-sided type 1 error rate of $\alpha=0.05$. The null hypothesis will only be rejected if the investigational drug demonstrates superiority. An unadjusted chi-square test will be used to test this hypothesis. The corresponding two-sided type 1 error rate is $\alpha=0.10$. Therefore, the null hypothesis will be rejected if the chi-square p-value is less than 0.10. The corresponding 90% two-sided confidence interval will be provided. The lower bound of the 90% confidence interval is equivalent to the lower bound of a 1-sided 95% confidence interval. Based on the study data, it can be concluded that the true difference in success rates is at least equal to the lower bound of the 1-sided 95% confidence interval.

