8.1 Primary AKI Endpoint

The numbers and percentages of patients in each group meeting the primary efficacy endpoint of complete recovery (*freedom from durable loss of renal function at Day 28*) is summarized in Table 14.2.1.1 for the mITT (primary efficacy) analysis set. This table also includes the statistical significance of this endpoint based on an unadjusted chi-square statistic. Study success requires one-sided $p \leq 0.05$ for this endpoint which is equivalent to a two-sided $p \leq 0.10$ as long as the percentage of subjects achieving the endpoint is larger in the actively treated group compared to placebo. This table also provides the estimated treatment group difference and 90% confidence interval corresponding to the one-sided significance level. The lower bound of the 90% confidence interval is equivalent to the lower bound of a 1-sided 95% confidence interval. Based on the study data, it can be concluded that the true difference in success rates is at least equal to the lower bound of the 1-sided 95% confidence intervals. Table 14.2.1.1 also provide the same summaries for the components of the primary endpoint.

- Alive at Day 28,
- Free of dialysis at Day 28, and
- Less than a 37% loss of estimated Glomerular Filtration Rate (eGFR; measured with the Modification of Diet in Renal Disease (MDRD) formula from the patient's reference eGFR) at Day 28.

Table 14.2.1.2, and 14.2.1.3 repeat these analyses in the AT and PP analysis sets, respectively.

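### The SAP tests the primary hypothesis at one-sided 0.05, the protocol at one-sided 0.025; the protocol synopsis also quotes 89% power where its own alpha gives 81.6%.

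*SAP*

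**What the plan says.** **Protocol.** The synopsis (Primary Analysis) reads "These hypotheses will be tested using an unadjusted chi-square test at a one-sided type 1 error rate of" 0.025, and section 12.5.1 repeats this. Section 12.5.2 and the title of Table 6 use the same level. Section 12.5.2 gives 81.6% power for 75% vs 50% with 120 patients. The synopsis sample-size text also states one-sided 0.025, but then says: "This sample size results in 89% power if the true success rates are 75% and 50% for the investigational drug and placebo, respectively".

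**SAP.** Section 2.1.1 reads "These hypotheses will be tested using a one-sided type 1 error rate of" 0.05, for the same hypothesis, endpoint and test. Section 2.1.2 bases its power table on 0.05, gives 89% for 75% vs 50%, and says power stays above 80% down to a 22-point difference. Section 5.2 spells out the decision rule: "Therefore, the null hypothesis will be rejected if the chi-square p-value is less than 0.10". Section 8.1 repeats the success criterion and sets the reporting: "This table also provides the estimated treatment group difference and 90% confidence interval corresponding to the one-sided significance level".

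**Precedence.** SAP section 1: "When differences exist in descriptions or explanations in the Clinical Study Protocol and this SAP, the SAP prevails".

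**The concern.** The 0.05 level is not a stray typing error. It appears in four SAP sections, with its two-sided equivalent, a matching confidence interval and a matching power table. Under the precedence clause it would govern, so the primary claim would be made at twice the nominal error rate that the protocol states. Neither document acknowledges the difference.

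Any result favouring active with two-sided p between 0.05 and 0.10 is a success under one document and a failure under the other. The interim analysis is also touched. Protocol 12.5.3 promises control of type 1 error at the desired nominal value, and the two documents name two such values. Finally, a reader of the synopsis alone is told that power is 89% at a level where it is not.

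**Working it through.** **Inputs.** 60 per arm, 1:1, control rate 0.50, active rate 0.75, no loss of patients because of LOCF (protocol 12.5.2, SAP 2.1.2). Alpha is one-sided 0.025 (protocol) or 0.05 (SAP).

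**1. Reproducing the stated power.** Normal approximation with pooled variance under the null:

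power = Φ[(d − z·s0)/s1], with s0 = √(2·p̄(1−p̄)/n) and s1 = √((p1(1−p1)+p0(1−p0))/n).

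For 0.75 vs 0.50: p̄ = 0.625, s0 = 0.0884, s1 = 0.0854.

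- z = 1.960: (0.25 − 0.1732)/0.0854 = 0.899, power **0.816**.
- z = 1.645: (0.25 − 0.1454)/0.0854 = 1.225, power **0.890**.

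All 48 cells of protocol Table 6 reproduce at 0.025 (largest difference 0.0005), and all seven rows of SAP Table 1 reproduce at 0.05. Each table is right for its own alpha.

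**2. The synopsis figure.** At 0.025 no usual method gives 89%: pooled 0.816, unpooled 0.833, arcsine 0.818, continuity-corrected 0.759, exact 0.818, exact with continuity correction 0.760. The 89% is the 0.05 value.

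**3. The 22-point statement.** At 72% vs 50%, power is 0.802 at 0.05 and 0.700 at 0.025 (also the Table 6 entry). The difference detectable with 80% power is 22.0 points at 0.05 and about 24.5 points at 0.025.

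**4. Where the verdicts part.** Placebo 30/60, Pearson chi-square without continuity correction, Wald intervals in percentage points:

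| Active | Difference | z | Two-sided p | 90% CI | 95% CI | SAP | Protocol |
|---|---|---|---|---|---|---|---|
| 38/60 | 13.3 | 1.474 | 0.141 | −1.4 to 28.1 | −4.2 to 30.9 | fail | fail |
| 39/60 | 15.0 | 1.662 | 0.097 | 0.3 to 29.7 | −2.5 to 32.5 | success | fail |
| 40/60 | 16.7 | 1.852 | 0.064 | 2.1 to 31.3 | −0.7 to 34.1 | success | fail |
| 41/60 | 18.3 | 2.043 | 0.041 | 3.8 to 32.8 | 1.1 to 35.6 | success | success |

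**5. Exact probabilities.** Full binomial enumeration, 60 per arm, control 0.50. The last column is P(1.645 < z ≤ 1.960).

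| Active rate | Reject at 0.025 | Reject at 0.05 | Verdicts differ |
|---|---|---|---|
| 0.50 (null) | 0.027 | 0.055 | 0.027 |
| 0.60 | 0.204 | 0.313 | 0.109 |
| 0.66 | 0.436 | 0.579 | 0.143 |
| 0.70 | 0.618 | 0.747 | 0.129 |
| 0.75 (design) | 0.818 | 0.897 | 0.079 |

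Protocol 12.5.3 regards 66% vs 50% as still clinically meaningful.

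**6. Conditional power.** Current trend, n1 = 80 of n2 = 120:

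CP = Φ[(z1·√(n2/n1) − z)/√(1 − n1/n2)].

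- Observed 0.66 vs 0.50: z1 = 0.16/√((0.2244+0.25)/40) = 1.469. CP = Φ[(1.799 − 1.960)/0.577] = 0.3905 at 0.025, and Φ[(1.799 − 1.645)/0.577] = 0.606 at 0.05.
- Observed 0.65 vs 0.50: z1 = 1.373. CP = 0.3148 at 0.025 and 0.525 at 0.05.

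The two values printed in protocol 12.5.3 are the 0.025 values.

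**The case against.** The strongest reply is that the operative rule is not in doubt. The SAP prevails, will be finalised before unblinding, and is internally consistent at 0.05. Only one rule would be applied, so differing verdicts compare the SAP with text that it overrides. The SAP also looks like the later document: section 3.10.6 calls ATB-202 recently completed, while protocol 7.1 calls it ongoing. The change may be deliberate, and SAP section 10 promises that deviations will be justified in the final report. The SAP's front pages were not available to me.

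Much of this stands. Nothing in the documents shows that 0.05 was a mistake, and the SAP's 22-point statement and the protocol's conditional powers are each correct at their own alpha. The 14.3% is close to the peak of the disagreement; at the planned effect it is 7.9%. The only wrong power sentence is in the synopsis, and the protocol body already has the right figure.

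It does not remove the problem. A precedence clause decides which text wins; it gives no reason for relaxing the primary error rate and leaves the protocol saying something else. A justification in the final report comes after unblinding.

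**Conclusion.** The conflict is real and must be resolved before unblinding. The nominal one-sided error rate doubles from 0.025 to 0.05; exact size at a common 50% rate goes from 2.7% to 5.5%. Both documents restrict rejection to superiority of active, so the SAP rule is a 5% one-sided test, not a 10% false-positive rate. The synopsis overstates power by 7.4 points (89% against 81.6%), a smaller error that follows from the same mismatch.

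The cut-offs and probabilities assume exactly 60 analysed per arm, and the cut-offs also assume 30/60 on placebo. Exclusions from the analysis set or a sample-size increase would shift them, but not the factor of two in nominal alpha. These are fixed-design figures; the Promising Zone bounds were not recomputed.

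**What to change.** State one alpha in both documents before unblinding.

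**Default, one-sided 0.025.**
- Change SAP 2.1.1, 2.1.2, 5.2 and 8.1 to one-sided 0.025: two-sided p<0.05 in favour of active, with a 95% confidence interval.
- Replace SAP Table 1 with the N=120 column of protocol Table 6, restate the SAP's 89% as 81.6%, and delete the 22-point sentence.
- Correct the synopsis power to 81.6%.
- Confirm that the interim conditional power uses 0.025, as the protocol's printed values already do.

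This costs SAP wording and one protocol sentence, which still has to go through the change process in protocol 15.3.1. No patients are added if 81.6% is accepted. Keeping 89% at 0.025 needs 75 per arm (power 0.893), that is 150 patients instead of 120.

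**Alternative, one-sided 0.05.** Amend the protocol with a reason for the higher error rate. Recompute Table 6 (for example 0.890 at 75% vs 50% with N=120, 0.897 at 71% vs 50% with N=180, 0.898 at 66% vs 50% with N=320) and the conditional powers (0.606 and 0.525). Recheck the Promising Zone lower bounds and the statement in 12.5.3 that an observed difference of about 0.15 is needed before expansion is allowed. The cost is a substantive protocol amendment.
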